#### **7.6. Subgroups**

Subgroup analyses only apply to some of the exploratory endpoints and are described in section [9.2.3](#).

This document is confidential.

## 8. Demographic, Other Baseline Characteristics and Medication

### 8.1. Patient Disposition and Withdrawals

Listings of treatment assignments, including the subject's identification, date of randomization, and assignment to treatment, will be presented.

The following frequencies (number and percent) will be displayed for all patients in the screened population: patients screened, patients randomized, screen failures, and reasons for screen failure.

The analysis populations will be summarized with counts and percentages by treatment. This table will include the following: number of patients in screened population, patients in safety population, reasons for exclusion from the safety population, patients in Intent-to-Treat population, reasons for exclusion from the Intent-to-Treat population, patients in Per-Protocol population, and reasons for exclusion from the Per-Protocol population.

The following frequencies (number and percent) will be displayed for all patients in the randomized population: randomized patients, patients in the safety population, patients in Intent-to-Treat population, patients in Per-Protocol population, patients who completed the study (including follow-up), patients who discontinued early, patients who completed study treatment, patients who discontinued study treatment early also presented by reason for early discontinuation and study duration in days. The denominators will be the number of randomized patients. A Kaplan-Meier plot of time to discontinuation of study treatment will be presented by treatment for the ITT population.

Completion/discontinuation status, inclusion/exclusion criteria definitions and Inclusion/exclusion criteria violations will be listed by patient.

### 8.2. Protocol Deviations

All protocol deviations (minor and major) observed during the conduct of the study will be listed. Major protocol deviations (patients with at least one major PD overall and split by PD category, patients with at least one minor PD overall and split by PD category) will be summarized by treatment group for all randomized patients.

### 8.3. Demographic and Baseline Characteristics

Demographic and baseline characteristics, including age, sex, child-bearing potential, race, ethnicity, PsA, disease duration, height, body weight and body mass index (BMI) will be summarized for the ITT population using standard descriptive statistics. This table will be repeated for the PP population.

A summary table will be provided for previous psoriasis treatments (e.g. prior systemics, biologics). Previous psoriasis treatments and reasons for stopping previous psoriasis treatments will be summarized for the ITT population. Baseline efficacy assessments: PASI, IGA, PSS, BSA, DLQI score, PGA-F, ss-IGA, scalp itch NRS and [REDACTED] will be summarized for the ITT population. No formal statistical comparisons between populations will be performed. Demographics will be listed for all patients in the randomized population.

### 8.4. Smoking and Alcohol History

Smoking and alcohol history will be summarized for the ITT population using standard descriptive statistics and listed for all patients in the randomized population.

This document is confidential.

## **8.5. Medical History**

Medical history, including surgical history will be coded using Medical Dictionary for Regulatory Activities (MedDRA) 24.0. Past Medical history and ongoing conditions will be summarized in separate tables for the ITT population presenting the number and percentages of patients within each preferred term (PT) grouped by the system organ class (SOC). A patient with multiple occurrences of an event in a PT is counted only once. Medical history will be listed for all patients in the randomized population.

## **8.6. Medication**

The WHO Drug, March 2021, B3 will be used to classify prior and concomitant medications by therapeutic class and drug name.

Prior medication is defined as any medication taken before the date of the first dose of study treatment. Concomitant medication is defined as any medication taken on or after the date of the first dose of study treatment.

The use of prior medications, concomitant medications and concomitant disallowed medications will be summarized by the number and percentage of patients for the ITT population. If a patient takes a specific medication multiple times or takes multiple medications within a specific therapeutic class, that patient would be counted only once for the coded drug name or therapeutic class.

Prior and concomitant medications will be listed for all patients in the randomized population.

## **8.7. Extent of Exposure**

Study drug administration data including dates for administration, dispensing and dose interruption details will be listed for all patients in the ITT population.

## **8.8. Treatment Compliance**

When patients receive the study drug at the site, they will receive it directly from the investigator or designee who will also give instruction for dose administration. The date of study drug dispensed to the patients will be recorded. At all site visits, patients will return all study drug, including packaging, dispensed at the previous visit.

The dose of study drug and study patient identification will be confirmed at the time of administration by a member of the study site staff other than the person administering the study drug.

When patients self-administer the study drug at home, compliance with the protocol will be assessed at each visit. Compliance will be assessed by direct questioning and counting returned tablets during the site visits. Deviation from the prescribed dosage regimen should be recorded..

A record of the quantity of study drug dispensed to and administered by each patient must be maintained and reconciled with study drug and compliance records. Study drug administration dates, including dates for administration delays and/or dose reductions will also be recorded.

Number of patients with missed doses, number of missed doses, days of dosing, reasons doses were missed and compliance rate will be summarized overall by treatment for the ITT population and separately for the titration period..

This document is confidential.

## 9. Efficacy

For inferential analyses of primary and secondary efficacy endpoints, each active treatment group will be compared with the placebo group.

Primary and secondary efficacy endpoints are to be assessed in the ITT Population. Missing data for the primary analysis of primary and secondary binary endpoints will be handled with the following multiple imputation method: Intermittent missing data will first be imputed using the MCMC method implemented with the SAS MI procedure, which is appropriate for non-monotonic missing data. Data missing after patients discontinue treatment early will then be multiply imputed with the SAS MI procedure using a regression statement (number of imputations: 50, seed: 5863781). At each time point, missing data will be assumed to be MAR and to follow a distribution similar to scores for patients who are still in the study and randomized to the same treatment group.

For categorical efficacy endpoints based on a continuous variable, the multiple imputation will be first done for the continuous variable, then determine the category using the imputed values. Efficacy analyses will be repeated on the PP Population for primary and secondary endpoints.

When appropriate, the raw parameter, its change from Baseline, and percentage change from Baseline will be summarized.

### 9.1. Primary Efficacy Endpoint and Analysis

The primary endpoint in this study is the percentage change in PASI score from Baseline at Week 16.

The primary endpoint (primary analysis) will be analyzed using analysis of covariance (ANCOVA) with treatment group as factor and Baseline PASI as covariate. Each active treatment dose will be compared with placebo. No adjustment for multiplicity will be made and the 0.05 level of significance will be used to claim efficacy compared with placebo. Least square means and the 95% confidence interval of the difference between each active treatment and placebo will be calculated.

The primary analysis set will be the ITT population with multiple imputation approach to handle missing values. The same analyses will be repeated for Weeks 20, 12, 8 and 4. These analyses will be repeated on the PP population.

LSMean (+/-SE) percentage change of PASI score will be presented graphically over time from Baseline to Week 4, 8, 12, 16 and 20.

Actual values, change from baseline values and percentage change from baseline of PASI will be summarized by visit using descriptive statistics and presented graphically over time.

The mixed model for repeated measures (MMRM) will be used as a supportive analysis. To ensure that all patients are included in the analysis, the baseline value for patients with no post-baseline data should be carried forward as the first post-baseline assessment, corresponding to imputing a change of 0 at the first post-baseline assessment. The MMRM model will be implemented using SAS PROC MIXED with treatment group, visit and treatment-by-visit interaction as factors and baseline PASI score by-visit interaction as a covariate. A restricted maximum likelihood (REML) will be used. The Kenward-Roger approximation will be used to estimate the denominator degrees of freedom and adjust standard errors. Least Squares Means Estimates and 95% confidence intervals will be given for each treatment group and for the difference between treatment groups (here also p-values will be presented).

This document is confidential.

PASI (including change from baseline values, percentage change from baseline values, PASI50, PASI75, and PASI90) will be listed.

## **9.2. Secondary Efficacy Endpoints and Analyses**

Continuous secondary efficacy endpoints will be analyzed based on observed data using MMRM, using a modelling approach assuming MAR for missing data. These analyses will be repeated on the PP population.

The binary secondary efficacy endpoints will be analyzed using differences in proportions, comparing each active treatment group to placebo in the ITT population with handling of missing data as specified in Section 9. Response by treatment group and difference in response rate and p-values compared to placebo will be presented.

The secondary endpoints and the percentage change of BSA will be presented graphically over time from Baseline to Week 20. In addition, shift tables will be provided between Baseline and each visit for the IGA distribution. The PASI percentage changes from Baseline will be plotted to identify where the best separation between treatments occur. These figures and tables are based on observed cases, thus purely descriptive.

### **9.2.1. Key Secondary Endpoints**

- Patients achieving 75% reduction in PASI (PASI75) response at Week 16.
- Patients achieving a score of Clear (0) or Almost Clear (1) and an at least 2-point improvement in IGA at Week 16.

In addition to absolute PASI scores, response to treatment is presented as a percentage response rate: PASI50, PASI75 and PASI90. PASI75 represents the percentage of patients who have achieved a 75% or more reduction in their PASI score from baseline.

The key secondary endpoints (primary analysis) will be analyzed using differences in proportions, comparing each active treatment group to placebo in the ITT population. Response by treatment group and difference in response rate and p-values compared to placebo will be presented. As supportive analysis, this analysis will be repeated, with handling of missing data as non-response. In case of baseline imbalance in baseline disease severity between treatment groups an additional supportive analysis stratifying for baseline disease severity using a Cochran-Mantel-Haenszel (CMH) test will be performed. Actual values of IGA will be summarized by visit using descriptive statistics and presented graphically over time. The percentage of patients with PASI75 and the percentage of patients achieving clear (0) or almost clear(1) will be presented graphically over time. These tables and figures are based on observed cases, thus purely descriptive.

### **9.2.2. Other Secondary Endpoints**

- Patients achieving a score of Clear (0) or Almost Clear (1) and an at least 2-point improvement in IGA at Weeks 4, 8, 12, and 20.
- Patients achieving PASI75 response at Weeks 4, 8, 12, and 20.

**This document is confidential.**

- Patients achieving 50% reduction in PASI (PASI50) and 90% reduction in PASI (PASI90) response at Weeks 4, 8, 12, 16, and 20.
- Change from Baseline in PASI at Weeks 4, 8, 12, and 20.
- Change from Baseline in total Psoriasis Symptoms Scale (PSS) score at Weeks 4, 8, 12, 16, and 20.
- Change from Baseline in each individual item of the PSS at Weeks 4, 8, 12, 16, and 20.
- Change from Baseline in the affected body surface area (BSA) at Weeks 4, 8, 12, 16, and 20.
- Change from Baseline in Dermatology Life Quality Index (DLQI) score at Weeks 16 and 20.
- Patients experiencing psoriasis rebound by Week 20, defined as PASI  $\geq$ 125% of Baseline or new generalized pustular, erythrodermic, or more inflammatory psoriasis.

PASI50 represents the percentage of patients who have achieved a 50% or more reduction in their PASI score from baseline. PASI90 represents the percentage of patients who have achieved a 90% or more reduction in their PASI score from baseline.

Continuous secondary efficacy endpoints will be analyzed using MMRM, similar to the supportive MMRM for the primary endpoint. The same analyses will be repeated on the PP population.

The analysis on categorical secondary efficacy endpoints will be performed using differences in proportions, comparing each active treatment group to placebo in the ITT population with handling of missing data as specified in Section 9. Response by treatment group and difference in response rate and p-values compared to placebo will be presented.

Actual values and change from baseline values of PSS will be summarized by visit using descriptive statistics and presented graphically over time. Actual values, change from baseline values and percentage change from baseline of BSA and DLQI will be summarized by visit using descriptive statistics and presented graphically over time. The percentage of patients with PASI50 and PASI90 will be presented graphically over time. These tables and figures are based on observed cases, thus purely descriptive.

PSS (including change from baseline values) will be listed. BSA and DLQI (including change from baseline and percentage change from baseline values) will be listed.

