After a Screening visit up to 28 days before Baseline, approximately 200 patients will be assigned randomly in a 1:1:1:1 ratio to receive 1 of the 3 orismilast doses (20 mg, 30 mg, or 40 mg) or placebo twice daily (BID) for 16 weeks, with a 4-week Follow-up visit. Administration will begin at Baseline with a dose titration period. The maximum duration of study participation is approximately 24 weeks.

Patients will be seen at the site on Screening, Baseline (Day 1), and Weeks 1, 2, 4, 8, 12, 16 (End-of-Treatment visit), and 20 (Follow-up visit, 4 weeks after treatment completion or discontinuation). Visits at Weeks 1 and 2 could be conducted via a telemedicine procedure at Investigator's discretion.

At Baseline and each visit from Week 4 onwards, PASI, BSA, IGA, and PSS will be assessed. Quality of life will be assessed by administration of DLQI at Baseline and at Weeks 16 and 20 visits. Additional efficacy parameters include: an ss-IGA, a Physician Global Assessment of fingernail psoriasis (PGA-F), and

These parameters will be assessed at Baseline and Weeks 16 and 20. Safety evaluations include adverse events (AEs), laboratory and vital sign assessments, physical examinations, as well as mood change evaluation by patient (Hospital Anxiety and Depression Scale) and suicidal ideation evaluation by Investigator (C-SSRS). A panel of cardiovascular risk factors will be assessed at Baseline and Week 16.

Before administration of the study drug at Baseline and on Weeks 4, 8, and 16, blood will be collected for orismilast concentration determination.

Selection of Patients:

Main Inclusion Criteria:

- 1. Capable of giving signed informed consent, which includes compliance with the requirements and restrictions listed in the Informed Consent Form (ICF) and in the protocol.
- Male and female patients ≥18 years of age at the time of signing the ICF.
- 3. Body weight of >40 kg at the time of signing the ICF.
- 4. Diagnosis of chronic, stable plaque-type psoriasis at least 2 months before the Screening visit. If the patient is diagnosed with psoriasis arthritis, the arthritis should be stable.
- 5. Moderate-to-severe plaque-type psoriasis as defined by PASI \geq 12, BSA \geq 10%, and IGA \geq 3 at the screening and baseline visits.
- 6. Candidate for systemic antipsoriatic treatment or phototherapy.

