15.3.1. Analysis of Primary Efficacy Endpoint

The primary endpoint, percentage change from Baseline to Week 16 in PASI, will be analyzed using analysis of covariance with treatment group as factor and Baseline PASI as covariate. As a supportive analysis, a mixed model for repeated measure (MMRM) will be performed with treatment group, visit and treatment-by-visit interaction as factors and Baseline PASI score by-visit interaction as a covariates.

Each active treatment dose will be compared with placebo. No adjustment for multiplicity will be made and the 0.05 level of significance will be used to claim efficacy compared with placebo. Least square means and the 95% confidence interval of the difference between each active treatment and placebo will be calculated. The primary analysis set will be the ITT Analysis Population with multiple imputation approach to handle missing values. The same analyses will be repeated for Weeks 20, 12, 8 and 4.

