15.3.2. Analysis of Secondary Efficacy Endpoints

For continuous secondary efficacy endpoints including change from Baseline in PASI, total PSS, each individual item of the PSS, BSA and DLQI, a MMRM will be performed similar to the supportive MMRM for the primary endpoint.

The key secondary efficacy endpoints and other binary secondary efficacy endpoints (IGA success, PASI50, PASI75, PASI90) will be analyzed using the Mantel-Haenszel (MH) test, comparing each active treatment group to placebo in the ITT Analysis set.

For categorical endpoints, the MH procedure, with ridit scores, will be used; this test is the same as the nonparametric Wilcoxon test and enhances the analysis when the parameter is not normally distributed. Graphics will be added to facilitate interpretation. IGA scores/full scale will be analyzed using the MH test and the row mean score statistics and the ridit transformation.

The above endpoints (PASI changes and percentage changes, IGA success, PASI50, PASI75, PASI90) and the percentage change of BSA will be presented graphically over time from Baseline to Week 20. In addition, shift tables will be provided between Baseline and each visit for the IGA distribution. The PASI percentage changes from Baseline will be plotted to identify where the best separation between treatments occur.

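### Read literally, the MMRMs for change in PSS, BSA and DLQI adjust for baseline PASI only; the endpoint's own baseline is collected but named nowhere as a covariate

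*SAP*

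**What the plan says.** SAP Section 9.2.2 gives the analysis of the continuous secondary endpoints in one sentence: "Continuous secondary efficacy endpoints will be analyzed using MMRM, similar to the supportive MMRM for the primary endpoint". Protocol Section 15.3.2 lists the endpoints and points to the same model: "change from Baseline in PASI, total PSS, each individual item of the PSS, BSA and DLQI, a MMRM will be performed similar to" the supportive one for the primary endpoint.

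That supportive model is written out in SAP Section 9.1, "with treatment group, visit and treatment-by-visit interaction as factors and baseline PASI score by-visit interaction as a covariate". Protocol Section 15.3.1 has the same covariate: "Baseline PASI score by-visit interaction as a covariates".

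No visible section of either document names baseline PSS, BSA or DLQI as a covariate. The values exist. Protocol Section 2 states: "At Baseline and each visit from Week 4 onwards, PASI, BSA, IGA, and PSS will be assessed". It and the schedule of assessments (Protocol Table 4) also place DLQI at Baseline, Week 16 and Week 20. SAP Section 8.3 lists what will be summarized at baseline: "Baseline efficacy assessments: PASI, IGA, PSS, BSA, DLQI score, PGA-F, ss-IGA, scalp itch NRS".

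**The concern.** A change score is tied to its own starting value. Patients who start high have more room to fall, and a patient whose DLQI or PSS item starts near zero cannot improve. Baseline PASI is only a partial stand-in. The inclusion criteria set a minimum for PASI, BSA and IGA but none for DLQI or PSS, so the patient-reported scales can start anywhere in their range.

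A programmer who copies the Section 9.1 model would leave out the natural prognostic covariate for each of these endpoints. One who reads the cross-reference more loosely would put it in. The two models give different estimates, standard errors and p-values, and the SAP does not say which is meant.

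At stake are the width of the intervals and the handling of chance imbalance between arms of about 50. The affected endpoints include every patient-reported secondary outcome, and they feed the secondary objective of choosing the dose with the best benefit/risk. DLQI has a further weakness: with no assessment between Baseline and Week 16, a patient who leaves early has little DLQI information other than the baseline value. The missing-at-random assumption in SAP Section 9.2 is more plausible when the model conditions on that value.

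**Working it through.** **The plan's own figure.** The only power statement is for the primary endpoint (Protocol Section 15.1, SAP Section 4.3): means of -32.2% and -50.9%, SD 33%, 50 per arm, two-sided 5%, 80% power. The difference is 18.7 points and the standard error is 33 × √(2/50) = 6.6, so the noncentrality is 18.7/6.6 = 2.83. The exact noncentral t gives 80.1%, so the figure reproduces. No SD, correlation or power is given for PSS, BSA or DLQI, and everything below rests on assumed values.

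**Set-up.** With complete data, an MMRM whose terms all interact with visit gives the same treatment estimate at a visit as an ANCOVA at that visit, so single-visit algebra is enough. Take the baseline SD as 1 and let
- k = follow-up SD divided by baseline SD,
- ρ = correlation of the endpoint's own baseline with its follow-up value,
- a = correlation of baseline PASI with the endpoint's own baseline.

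Baseline PASI is assumed to relate to follow-up only through the own baseline.

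**Formulas for the variance of the change score.**
- Unadjusted: k² + 1 − 2ρk
- Adjusted for baseline PASI only: k² + 1 − 2ρk − a²(1 − ρk)²
- Adjusted for own baseline: k²(1 − ρ²)

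**Equal SDs (k = 1).** Example at ρ = 0.5, a = 0.4: PASI-only 1 − 0.16 × 0.25 = 0.96; own baseline 0.75; cut 1 − 0.75/0.96 = 21.9%. The power column shows what an effect with 80% power under the PASI-only model would have under the own-baseline model, at 50 per arm (noncentral t).

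| ρ | a | PASI-only | Own baseline | Variance cut | Power, from 80% |
|---|---|---|---|---|---|
| 0.3 | 0.2 | 1.3804 | 0.91 | 34.1% | 93.2% |
| 0.3 | 0.6 | 1.2236 | 0.91 | 25.6% | 90.1% |
| 0.5 | 0.2 | 0.9900 | 0.75 | 24.2% | 89.6% |
| 0.5 | 0.6 | 0.9100 | 0.75 | 17.6% | 87.0% |
| 0.7 | 0.2 | 0.5964 | 0.51 | 14.5% | 85.8% |
| 0.7 | 0.6 | 0.5676 | 0.51 | 10.1% | 84.0% |

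**Unequal SDs.** The two ends of the grid over k = 0.8 to 1.2 are:
- k = 0.8, ρ = 0.3, a = 0.2: PASI-only 1.16 − 0.04 × 0.76² = 1.1369; own baseline 0.64 × 0.91 = 0.5824; cut 48.8%.
- k = 1.2, ρ = 0.7, a = 0.6: PASI-only 0.76 − 0.36 × 0.16² = 0.7508; own baseline 1.44 × 0.51 = 0.7344; cut 2.2%. Here power of 80% becomes only 80.9%.

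The direction is favourable at every point of the grid, but the size is not pinned down.

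**Chance imbalance.** If two arms differ by d in the own baseline, the expected follow-up difference due to that is ρkd, so the change score keeps (1 − ρk)d in absolute size. With equal SDs that share is 1 − ρ: 70%, 50% and 30% at ρ = 0.3, 0.5 and 0.7. Adjusting for PASI reduces it further, on average by the factor 1 − a². One standard error of a baseline difference at 50 per arm is √(2/50) = 0.2 SD. At ρ = 0.5 this leaves 0.5 × 0.2 = 0.10 SD before PASI adjustment, and 0.10 × (1 − 0.36) = 0.064 SD at a = 0.6.

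**The case against.** The strongest counter-argument is textual. Section 9.2.2 calls the model similar, and its next sentence says the same analyses will be repeated in the per-protocol population, so the authors had a word for identical and did not use it here. The Section 9.1 model cannot be copied outright in any case: its outcome is percentage change in PASI, and DLQI has only two post-baseline visits. Both primary models pair the outcome with its own baseline, and carrying that pairing over is a natural reading. The table shells are a separate document (SAP Section 21) and might name the covariate. This stands. A reader might infer that the plan definitely fixes baseline PASI as the sole covariate for PSS, BSA and DLQI, and the wording does not support that.

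A reader might also infer that the treatment comparisons are biased, or that a chance imbalance passes in full into the treatment difference. Neither follows. Randomization keeps the PASI-only comparison unbiased on average with complete data, and a change score has already subtracted the baseline, so only a part of the imbalance remains.

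The consequences are bounded. These are other secondary endpoints with nominal p-values (SAP Section 7.1). The primary endpoint, the key secondary endpoints and change in PASI are untouched. An imbalance would be visible in the baseline tables.

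What the objection does not remove is that the covariate is unnamed, and that the literal reading gives the less precise analysis. Seeing an imbalance in a table does not adjust for it.

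**Conclusion.** The point holds in a limited form. Read literally, the MMRMs for change in total PSS, PSS items, BSA and DLQI adjust for baseline PASI by visit and not for the endpoint's own baseline. The text also allows the matching baseline, so the defect is an unnamed covariate whose literal reading is the weaker choice.

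The loss under the literal reading is one of precision, plus a share of about 1 − ρ of any chance imbalance in the own baseline with equal SDs. The residual variance cut from own-baseline adjustment is about 10% to 34% for equal SDs, ρ of 0.3 to 0.7 and correlation with baseline PASI of 0.2 to 0.6. It is about 2% to 49% once the SD ratio may run from 0.8 to 1.2. For BSA the gain probably lies towards the low end, because PASI already scores affected area. A reader might take any one of these percentages as a property of this trial. The documents supply none of the inputs, so they are illustrations only.

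**What to change.** In SAP Section 9.2.2, replace the cross-reference with a statement that each continuous secondary endpoint is analysed by MMRM with treatment, visit, treatment-by-visit and the baseline value of the analysed endpoint (total PSS, the PSS item, BSA or DLQI) by visit as covariate. Baseline PASI by visit is used for the PASI models only.

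The cost is one SAP sentence before unblinding and one covariate changed per model. No new data are needed, because every one of these baselines is already collected and tabulated. If the authors always meant the matching baseline, the sentence simply records it.
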